### **Data and Safety Monitoring**

|€ For subjects who were not physically active prior to their neurologic injury, with intense exercise there is a possibility for increase in cardiovascular events such as stroke or heart attack.

|€ Patients with premorbid conditions will have close blood pressure and heart rate monitoring throughout the session by a skilled Doctor of Physical Therapy. There are physicians on site at TIRR Memorial Hermann in addition to skilled therapists that understand signs of poor exercise tolerance such as pallor, profuse sweating, headache, and lightheadedness. Patients with chest pain at any point during the study will have exercise immediately discontinued and will have all of their vitals signs including blood pressure, heart rate, and oxygen saturation checked on the spot. There are blood pressure cuffs and oxygen saturation monitors throughout all of the gyms and in all of the units at TIRR Memorial Hermann and TIRR Kirby Glenn.

|€ However, in the neurologic population that will be receiving the intervention, there is greater risk associated with remaining sedentary. Patients who do not receive intensive rehabilitation are at greater risk for pressure injury, deep vein thrombosis, Type 2 Diabetes, and obesity. Additionally, sedentary individuals are more likely to have low cardiorespiratory fitness, which is a well-known risk factor for chronic diseases.

|€ Additionally, literature published by the American Heart Association and the Neurologic Physical Therapy Association supports the implementation of high-intensity stepping training. Hornby et al has provided extensive research of high intensity stepping training on patients with stroke. Even though these patients have already had a cardiovascular-related event, even with interventions in which they are required to maintain their heart rate at 75-85% of HR Maximum, there were no increases in adverse events.

|€ Since this population will also be engaging in stepping training and locomotor training, there could be potential for increased risk of falls during interventions. However, therapists at the Memorial Hermann facility (which is where the study will be conducted) are highly experienced in walking interventions for these patients and in the prevention of falls. Additionally, most high intensity training stepping in patients with stroke, TBI, and SCI is proven to improve balance and thereby decrease risk of falls.

|€ For the more medically complex patients at TIRR inpatient (ie multiple comorbidities), a thorough chart review will be performed to ensure patient is not at increased risk of cardiovascular events (previous heart attacks, uncontrolled hypertension, etc). The Physical

Medicine and Rehabilitation Physician will also be asked to clear the patient for participation in high intensity training. For patients at Kirby Glenn outpatient, a chart review and medication review will be performed. If patient is at additional risk for cardiovascular event as determined by previous cardiac event or by uncontrolled hypertension as demonstrated by systolic blood pressure over 180 or diastolic blood pressure over 100 consistently, then the patient primary physician will be contacted to ensure the safety of high intensity training. Additionally, blood pressure and heart rate will be obtained before and after the intervention for every session. If patient has any signs of headache, nausea, vomiting, dizziness, blurred vision, double vision, or dysarthria during the treatment intervention, the treatment will be stopped immediately and vitals including blood pressure and heart rate will be taken.

- |€ In order to minimize fall risk, there will be a Doctor of Physical Therapy supervising the patient throughout the entire intervention. If the Doctor of Physical Therapy needs to leave even to get a blood pressure machine or a towel, the patient will take a seated rest break. -If any unplanned adverse events occur, or if protocol deviations occur, the PI of the study ([name]) will report these via the iRIS portal.
- |€ The PI of this study ([name]) will be responsible for reporting Serious Adverse Events and Unanticipated Problems to the IRB. The PI will also be responsible for maintaining the confidentiality of data, data collection, management, and analyses. The Primary Investigator will perform reviews of all data once every two weeks in order to ensure safety for all patients and to ensure all data is being tracked accurately.

## Statistics

- |€ Statistics will be utilized to compare outcome measures before and after the intervention. A dependent sample t-test will be used for comparison of pre- and post-intervention outcomes. MANOVAs will be utilized in order to determine potential differences in outcomes in patients with different diagnoses (ie grouping patients based on chronicity, nature of cerebellar disease) and to compare the four outcome measures that I will utilize. I may also consider doing multiple t-tests or multiple ANOVAâ€™s if the data does not meet statistical assumptions. However, I would just need to account for increased possibility of type 1 error.
- |€ Sample size will be 15 patients.

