## Objectives

|€ Primary objective: To determine the effects of high intensity stepping training on gait outcome measures in patients with cerebellar ataxia.

|€ Secondary objectives:

- Identify the correlations between gait outcome measures and measures of ataxia and balance in individuals with cerebellar ataxia.
- Determine differences in response to high intensity stepping training based off of diagnosis.

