## Study Population

[figure not shown]
|€ The sample will consist of all patients with a diagnosis of ataxia who were admitted to TIRR TMC Inpatient or TIRR Kirby Glenn Outpatient. Diagnoses of inclusion will include any pathology that primarily affects the brain/ cerebellum including degenerative diseases, stroke, TBI, posterior fossa tumor, and MS. Additionally patients will be ambulatory at initial evaluation or will have functional ambulation goals at initial evaluation (as noted by 10 meter walk test and 6 minute walk test measures documented as 0). The ages that will be included

in this study are patients ages 18-65 years old and the chronicity of injury will be of at least 1 month or greater.

- |€ The exclusion criteria include diagnoses that may have cerebellar involvement but without cerebellar ataxia as a principal impairment such as autism, down syndrome, schizophrenia, etc. Additionally, patients who are nonambulatory or who are not able to participate in high intensity stepping training due to cardiac involvement (such as cardiac rehabilitation parameters) or due to orthopedic limitations (such as weight bearing parameters) will be excluded from the study.
- |€ The subjects will not be directly recruited. Subjects will be referred to do this study before or after their initial evaluation if they have an ICD 10 code indicating ataxia, are found to have gait ataxia, or have a neurologic injury to some part of their cerebellum based off imaging.

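### Chronicity is a continuous time since injury, but the plan groups it as if it were a diagnosis and states no cut; with 15 patients this costs power in a secondary analysis (minor point)

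*Combined protocol and SAP*

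**What the plan says.** Three sections bear on this.

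- **Objectives.** One secondary objective is "Determine differences in response to high intensity stepping training based off of diagnosis". Time since injury is not mentioned.
- **Study Population.** Eligible conditions include degenerative disease, stroke, TBI, posterior fossa tumor and MS. Time enters as an entry criterion: "the chronicity of injury will be of at least 1 month or greater". There is no upper limit and there are no categories.
- **Statistics.** "MANOVAs will be utilized in order to determine potential differences in outcomes in patients with different diagnoses", which the same sentence spells out as "grouping patients based on chronicity, nature of cerebellar disease". The fallback, if assumptions fail, is several t-tests or ANOVAs, which also need groups. The section adds "Sample size will be 15 patients".

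The document gives no cut-point, number of chronicity groups or reason for grouping. No analysis in it keeps time continuous.

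**The concern.** Chronicity is listed as a way of forming diagnosis groups, yet the eligibility criteria treat it as a length of time. Three things follow.

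1. Cutting a continuous time into groups treats patients on the same side of the cut as identical. In a sample of 15 that makes a real relation between time and change easier to miss.
2. With no cut stated, the analyst has to choose one. A choice made with the results in view inflates the false-positive rate.
3. Study Population speaks of chronicity of injury but admits conditions that are not injuries, such as degenerative disease and MS. The date that starts the clock for those patients is not defined, so their chronicity group is left to judgement.

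What is at stake is the reading of a secondary subgroup result.

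**Working it through.** **The plan's own figure.** The only figure is the sample size of 15. It comes without alpha, power, effect size or SD, so it cannot be reproduced, and this point does not dispute it.

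**Inputs**

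- n = 15 (Statistics).
- Two-sided alpha of 0.05: assumed, as none is stated.
- Outcome: the change score on one measure: assumed. The MANOVA's power would also depend on correlations among the four outcomes, which are not given. One outcome isolates the cost of grouping.
- True correlation r between time (on a suitable scale, such as log months) and change: assumed 0.3, 0.5 and 0.7, with a linear relation and normal errors. The documents give no correlation.

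**Step 1: loss in principle.** In large samples, a median split of a normal variable multiplies its correlation with the outcome by √(2/π) = 0.80 and keeps 2/π = 0.637 of the information. For this question 15 patients then act like 15 × 0.637 = 9.5.

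**Step 2: power at n = 15, by simulation.** Two tests were run on the same data:

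- time kept continuous: t = r̂√(n − 2)/√(1 − r̂²), where r̂ is the sample correlation, on 13 df;
- a 7/8 split by time: t = (mean₁ − mean₂)/[s_p√(1/7 + 1/8)], also on 13 df.

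| Assumed r | Continuous | 7/8 split |
|---|---|---|
| 0.3 | about 19% | about 13% |
| 0.5 | about 50% | about 31% |
| 0.7 | about 88% | about 63% |

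Three groups of five do no better than the split: about 12%, 28% and 61%.

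**Step 3: false positives, r = 0.** The continuous test and a split fixed in advance both reject in about 5% of samples. If the cut with the smallest p-value is taken, the rate is about 16% with at least 5 patients per side and about 24% with at least 3. These rates are per outcome, before any allowance for four outcomes.

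**Step 4: where the continuous analysis does less well.**

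- Fewer dated patients: at r = 0.6, continuous power is about 70% with all 15 dated, 48% with 10 and 37% with 8. A split of the same 10 has about 28%, so within a fixed set of patients the continuous analysis still does better.
- A true threshold: if change jumps by 1.5 SD exactly at the 7/8 split, the split has about 76% power against 48% for the slope.

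**The case against.** The strongest reply is that this matters little. The primary hypothesis rests on the paired pre/post t-test, which is untouched. Chronicity appears once in the analysis plan, in a parenthesis, and no objective or hypothesis asks about time since injury. At modest correlations both analyses would usually miss the relation (19% against 13% at r = 0.3). The shape is assumed, and a threshold relation would favour a split at that threshold. A cut fixed in advance would also restore the 5% error rate without changing the method. All of this stands, and it is why the point is minor.

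It does not remove the point. The text does make chronicity a grouping factor, and the documents propose no threshold that would justify one. The remark "I would just need to account for increased possibility of type 1 error" concerns running several tests, names no method and does not cover the choice of a cut.

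Three stronger readings are tempting, and the documents support none of them.

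- *That the cut will be picked from the data.* The plan does not say so; it leaves the cut open.
- *That time and diagnosis will be analysed in separate one-way comparisons, leaving diagnosis confounded with time.* The text lists both factors and does not exclude a two-factor MANOVA. Time since onset may differ by diagnosis, but the documents give no data on that.
- *That the diagnosis comparison should therefore be adjusted for time.* Patients without a dated onset would drop out of an adjusted comparison. That could remove most or all of a diagnosis, such as degenerative disease, from the objective it is meant to serve.

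**Conclusion.** The point holds as a minor one. The plan treats a continuous time as a diagnosis grouping and states no cut. Under the stated assumptions, the loss of power from a 7/8 split is about 6, 19 and 25 percentage points at correlations of 0.3, 0.5 and 0.7 (19 − 13, 50 − 31, 88 − 63). The false-positive rate of 16% to 24% per outcome is conditional on a cut chosen after the data are seen.

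The power figures rest on assumed correlations, a relation linear on the chosen scale, normal errors and a usable date for all 15 patients. They would shrink with fewer dated patients and could reverse under a true threshold. A reader might infer that the main result is at risk. It is not, because the pre/post comparison does not use chronicity.

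**What to change.** In the Statistics section:

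1. Remove chronicity from the MANOVA grouping. Compare diagnoses by nature of disease only, keeping all patients.
2. Add a separate analysis, labelled exploratory: regress each change score on log(months since onset or injury). Report the slope with its 95% CI and the number of patients with a dated onset.
3. Before data are seen, define the start date for non-injury diagnoses, for example symptom onset or diagnosis.
4. Keep time out of the main diagnosis comparison. At most, show a time-adjusted version as a sensitivity analysis in dated patients.

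**Cost.** This is mostly wording. The onset or injury date must be recorded, not just confirmed as at least one month ago; a case report form is listed among the attachments, but its content is not available here, so whether it already captures the date should be checked. The regression assumes a log-linear shape, would be less sensitive than a well-placed split if there is a true threshold, and loses power if few patients can be dated.

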## Ethics

- |€ The PI is seeking IRB approval from both UTHealth Houston and Memorial Hermann.
- |€ An informed consent process will occur for all patients participating in this study (with the document attached). The consent process will inform the participants about the study, identify the risks and benefits, stress that participation is voluntary, and that the patient may choose to partake or stop at any time. The subjects will be informed that the intervention that they are getting focuses on intensity, and is already best clinical practice for many neurologic conditions.
- |€ In order to protect patient privacy, a linking log will be utilized instead of patient names linking them to a random number under which their data will be collected and stored securely, as per the â€œData handling and record keeping.â€
  - The only person with access to this log will be the primary investigator as the PI will be the only one collecting and organizing data.

### **Data handling and record keeping**

- |€ Names and data from participants will be transcribed to an identification number and kept on a master list that is kept by the principal investigator on a password protected computer or in a locked file cabinet at the PIâ€™s desk.
- |€ The identification number will be used to protect patient privacy while collecting their outcome measure data.

### **Quality control and assurance**

- |€ In an effort to assure that data is collected accurately, a Polar Heart Rate monitor will be used for heart rate monitoring during each session.
- |€ Additionally, only the PI or another Doctor of Physical Therapy will be permitted to implement the intervention that is documented for research.
- |€ There will be no third-party monitoring.
- |€ In order to be sure that data is accurate and consistent, the PI will be the only person performing the initial outcome measures and the final outcome measures. Due to the extremely high levels of inter-rater reliability of the Six Minute Walk Test, 10 Meter Walk Test, SARA, and Berg Balance Scale, there will be high validity with data being collected by only one person.
- |€ Self-assessment will be performed by the primary investigator and the primary investigator will be the primary physical therapist documenting the interventions. Therefore, the PI will perform audits of the data after every week the study is being performed.
- |€ Due to the high objectivity of the outcome measures being utilized and heart rate monitoring during the intervention, third party monitoring is not currently necessary for this project.

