## Study Design

|€ The study will be a non-blinded prospective case series performed at TIRR Memorial Hermann and TIRR Kirby Glenn. Participants will be recruited if they have an ICD-10 code of ataxia or present with ataxia at initial evaluation. Either the director of the brain injury rehabilitation team or the evaluating therapist will contact the principal investigator in order to refer the patient to the study. The evaluating therapist will provide the PI with the referral through a secure e-mail utilizing their Memorial Hermann e-mail. The secure e-mail will include the patient diagnosis and their room number with no other personal identifiers listed until the patient consents to the research study.

|€ The study sample will be about 15 and the expected duration of the study will be at least 3-4 weeks.

|€ The primary outcomes measured include the 10 Meter Walk Test and the 6 Minute Walk Test. These outcome measures will be performed once at baseline and again at week 3.

|€ The secondary outcomes to be measured include the SARA and the Berg Balance Scale. These outcome measures will be performed once at baseline and again at week 3.

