## Study Procedures

- |€ Potential subjects will be referred to the primary investigator upon arrival to TIRR Memorial Hermann Inpatient or TIRR Memorial Hermann Kirby Glenn outpatient, or after their initial evaluation is performed. The evaluating physical therapist will contact the primary investigator if a patient is presenting with physical symptoms of cerebellar ataxia. The evaluating physical therapist will contact the primary investigator through a secure email and will email [[contact]](mailto:[contact]). The e-mail will include secure in the heading, protecting patient information and data.
- |€ Informed consent will be obtained prior to participation in this study. The principal investigator will introduce the study to potential participants at initial evaluation or during their first physical therapy treatment session. Patients will be given the informed consent document and will be allowed to ask questions regarding the purposes, confidentiality, and procedures of the study.
  - If consent is obtained, all consent forms will be collected in a locked cabinet at the primary investigatorâ€™s desk.
- |€ The Six Minute Walk Test, 10 Meter Walk Test, SARA, and BBS will be recorded at initial evaluation and will also be collected by the primary investigator.
- |€ Each individual patient will receive 30 minutes of the high intensity stepping intervention 3 times a week for 3 weeks. Therefore, each participant will receive 9 sessions of high intensity stepping training, for a total of 4 hours and 30 minutes by the studyâ€™s conclusion.
- |€ Each intervention will occur with either the primary investigator as the physical therapist or as another Doctor of Physical Therapy providing care for that patient. If another Doctor of Physical Therapy is providing care for that patient, they will be instructed by the primary investigator on where to put interventions, heart rate monitoring, and blood pressure monitoring in the note. As the intervention is not extremely specific and since it is considered standard of care for patients with stroke, brain injury, and spinal cord injury, the primary investigator will not be required to be the only therapist providing the intervention for this study.

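### An unblinded investigator who also treats patients performs all four outcome tests at both visits, and the plan infers validity from inter-rater reliability, which cannot rule out a rater's expectation being counted as gain

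*Combined protocol and SAP*

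**What the plan says.** Study Design describes the study in these terms: "The study will be a non-blinded prospective case series performed at TIRR Memorial Hermann and TIRR Kirby Glenn". There is one group and no comparator. The primary outcomes are the 10 Meter Walk Test (10MWT) and the 6 Minute Walk Test (6MWT); SARA and the Berg Balance Scale are secondary. All four are taken at baseline and at week 3. The Statistics section compares them before and after with a dependent-sample t-test in 15 patients. The hypothesis, at the end of Background Information, is a significant improvement in the two walk tests.

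Quality control and assurance states that "the PI will be the only person performing the initial outcome measures and the final outcome measures". The reason given is accuracy and consistency. The section then appeals to extremely high inter-rater reliability of the four measures and concludes that "there will be high validity with data being collected by only one person". It adds that "the primary investigator will be the primary physical therapist documenting the interventions", that the PI audits the data weekly, and that no third party monitors the study. The last choice is defended as follows: "Due to the high objectivity of the outcome measures being utilized and heart rate monitoring during the intervention, third party monitoring is not currently necessary".

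On who treats, Study Procedures says: "Each intervention will occur with either the primary investigator as the physical therapist or as another Doctor of Physical Therapy providing care for that patient". It adds that "the primary investigator will not be required to be the only therapist providing the intervention for this study". Data and Safety Monitoring makes the PI responsible for data collection, management and analyses. The documents describe no masked, duplicate or video scoring and no script for the walk tests.

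**The concern.** Inter-rater reliability measures how closely different raters agree on the same performance. It is not validity, and it does not describe what one rater does on two occasions when that rater knows which visit is which, expects improvement and may have delivered the training. If anything the premise points the other way: where raters agree that closely, an independent rater would cost little precision.

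The appeal to objectivity and heart-rate recording does not close the gap. Heart-rate traces describe the training sessions, not any of the four outcomes. SARA and Berg depend on the rater's judgement. The walk tests are measured in distance and time, but performance can respond to how the patient is instructed and encouraged.

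At stake is the meaning of the main result. The plan claims a property for its data that the design does not provide, and a reader of the eventual report could take the pre-post change as free of assessor influence.

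**Working it through.** **The plan's own figure.** There is none to reproduce. The documents give a sample size of 15 but no significance level, sidedness, standard deviation, effect size or bias size.

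**Step 1: what the stated argument covers.**

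| Threat to the pre-post change | Does one rater at both visits deal with it? | Does high inter-rater reliability deal with it? |
|---|---|---|
| Different raters score differently | Yes | Yes, if reliability is as high as stated |
| The same rater scores or encourages differently at the final visit because improvement is expected | No | No |

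The second row is the one that remains.

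**Step 2: how a shift enters the estimate.** For each patient, observed change = true change + (rater effect at the final visit − rater effect at baseline). A constant leniency at both visits drops out. A shift between visits does not, and its mean is added in full to the mean change. The paired t-test has no term that could separate the two.

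**Step 3: how sensitive the test is (illustration).**

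Input from the documents: n = 15 (Statistics).

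Assumptions: two-sided level 0.05; no true change; normally distributed changes; a constant shift of b standard deviations (SD) of the change score towards improvement.

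- Critical value: t(0.975, 14 df) = 2.145.
- Smallest mean change declared significant: 2.145 / √15 = 2.145 / 3.873 = 0.554 SD of change.
- Chance of a false improvement: P(T > 2.145), with T noncentral t on 14 df and noncentrality b × √15.

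| b (SD of change) | b × √15 | Chance of a false improvement, per outcome |
|---|---|---|
| 0 | 0 | 2.5% |
| 0.05 | 0.194 | 3.8% |
| 0.1 | 0.387 | 5.5% |
| 0.25 | 0.968 | 14.5% |
| 0.5 | 1.936 | 43.8% |

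The table shows how the test responds to a shift of a given size. It does not estimate the shift in this study, and one value of b should not be read across all four outcomes.

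**Step 4: which outcomes are more exposed.** For SARA and Berg the rater assigns the score, so expectation can act on the score itself. For 6MWT and 10MWT it would act mainly through test conduct. A smaller b is therefore more plausible for the primary outcomes, though not b = 0 while no script is specified.

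**The case against.** The best case for the plan has four parts.

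*One rater is a sound choice in a before-after study.* It removes between-rater differences from the change score, and consistency is the reason the section gives first. This stands. The fault lies in the inference to validity, not in using one rater.

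*The PI need not treat everyone.* This also stands. Study Procedures allows another Doctor of Physical Therapy to deliver sessions, and the cover table expects therapists to be added. A reader might infer that the PI trains every patient and is the sole analyst. The documents do not support either: they call the PI the primary therapist documenting the interventions, and responsible for the analyses. Nor does the text say in terms that the weekly audit is of the outcome scores; it refers to the data.

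*The primary outcomes are objective.* This stands in part, as step 4 allows.

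*The study is openly non-blinded and small.* It is, and that keeps the point modest. But naming the design non-blinded in one section does not disclose the limitation when another section asserts high validity. The Publication Plan foresees possible journal submission and use of results by facilities.

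A reader might also infer that a control group would have cancelled the bias. It would do so only if the rater were masked to group or equally lenient to both. The absence of a control group is a separate weakness.

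**Conclusion.** The point holds in a limited form. An unblinded PI who also treats some or most of the patients performs every outcome test at both visits, and the step from inter-rater reliability to validity does not follow. The pre-post change therefore cannot be separated from assessor expectation, most plausibly in SARA and Berg and, through instructions and encouragement, in the two walk tests.

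The size is unknown. Under the assumptions in step 3, the chance of a false improvement ranges from 5.5% at a shift of 0.1 SD of change to about 44% at 0.5 SD, against 2.5% with no shift. It would be tempting to read the upper figures as the expected error rate of this study. The documents give no basis for that: the shift, the significance level and the sidedness are all assumed. The point should be addressed in the wording and test procedures; it does not call for a different design.

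**What to change.** 1. Use one fixed script of instructions and encouragement for the 6MWT and 10MWT, the same at both visits.
2. Score the final tests on a blank form, without consulting the baseline scores at that session, and lock the final scores before any comparison. Leave the heart-rate collection in Study Procedures, the two-weekly review in Data and Safety Monitoring and the weekly audit in Quality control and assurance as they are. Barring the PI from those data would conflict with those sections. This step reduces anchoring on the baseline score; it does not blind the PI or remove recall.
3. Where another Doctor of Physical Therapy already cares for the patient, let that therapist deliver the sessions and let the PI only test. Flag PI-treated patients in the results descriptively. With 15 patients and no random allocation of therapist, a formal comparison would tell little.
4. In Quality control and assurance, delete the inference from reliability to validity and the objectivity argument. State instead that outcomes were scored by an unblinded assessor who treated some of the patients, so that the pre-post change cannot be separated from assessor expectation.

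The cost is protocol wording, a script and a form, with no added staff or tests. The PI may treat fewer study patients, and the stated claim about the data becomes less favourable.
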